Official Title: A POST-MARKET, PROSPECTIVE, RANDOMIZED, CONTROLLED STUDY TO EVALUATE THE IOVERA® DEVICE

NCT Number: NCT03327220

Document Date: Protocol Revised Version (REV) 01 : 14 September 2017

**A POST-MARKET, PROSPECTIVE, RANDOMIZED, CONTROLLED STUDY TO
EVALUATE THE IOVERA® DEVICE IN TREATING PAIN ASSOCIATED WITH
TOTAL KNEE ARTHROPLASTY**

PROTOCOL NUMBER: MYO-1265 REV 01

VERSION: September 14, 2017

SPONSOR: Myoscience, Inc.
[name]
[name]
[contact] (office)
[contact] (fax)

SPONSOR REPRESENTATIVE(S): [name]
Director, Clinical Operations and Principal
Scientist

**The information contained in this document is confidential and proprietary property of
Myoscience, Inc.**

Revision	Description	DCO#	Release Date
01	• Initial Release	3269	10/02/2017

Investigator Protocol Signature Page (REV 01)

Read and initial below.

I understand this protocol contains information that is confidential and proprietary to Myoscience, Inc.

Any additional information added to this protocol is also confidential and proprietary to Myoscience, Inc. and must be treated in the same manner as the contents of this protocol.

I have read the entire protocol.

I understand what the protocol asks me to do as an Investigator.

I will conduct this study following this protocol and will make a reasonable effort to complete the study in the time noted.

I will provide this protocol to study staff under my direct supervision. My study staff will keep the protocol and associated documents confidential.

I will discuss this information with the study staff to ensure they are fully informed about the study and the test articles.

I will not start enrolling in this study until it is approved by a governing Institutional Review Board.

I understand the study may be terminated or enrollment suspended at any time by Myoscience, Inc., with or without cause, or by me if it becomes necessary to protect the interests of the study Subjects.

Name of Investigator

Investigator Signature

Date

Protocol Synopsis

Title	A Post-Market, Prospective, Randomized, Controlled Study to Evaluate the iovera [°] Device in Treating Pain Associated with Total Knee Arthroplasty
Study Device	iovera [°] (Myoscience Inc., Fremont, CA)
Study Objective	To evaluate the outcomes of patients undergoing iovera [°] treatment of the ISN and AFCN prior to total knee arthroplasty to provide temporary postoperative pain relief
Study Design	Single site, prospective, randomized
Treatment Groups	Pre-operative iovera [°] treatment vs. standard of care treatment
Duration of Participation	Up to 16 weeks (12 weeks post-op)
Study Population	Male or female, ages 22 to 79 scheduled to undergo a total knee replacement as a result of osteoarthritis
Total Number of Subjects	Up to 120 subjects (randomized 1:1)
Number of Sites	1
Study Procedures	iovera [°] treatment introducing temporary nerve conduction block of the ISN and AFCN
Data Collection Tools	
 • KOOS JR. • NRS for Pain
Primary Endpoint	Cumulative Opioid Consumption at 6 weeks post-TKA Surgery
Secondary Endpoints	
 • Changes from Baseline in KOOS JR. Scores through 6 weeks post-TKA • Changes from Baseline through 6 weeks post-TKA in NRS for Pain • Changes from Baseline through 6 weeks post-TKA in Timed Get Up and Go (TUG) test
Safety Assessment	
 • Adverse Event/Safety

Table of Contents

PROTOCOL SYNOPSIS.....	4
ABBREVIATIONS	7
1. BACKGROUND.....	8
2. REGULATORY STATUS.....	9
3. STUDY OBJECTIVE.....	9
4. STUDY DESIGN.....	9
5. DURATION	9
6. INVESTIGATOR QUALIFICATIONS	9
7. STUDY POPULATION.....	9
7.1 TARGET PATIENT POPULATION.....	9
7.2 SUBJECT ELIGIBILITY	9
8. STUDY DEVICE AND TREATMENT PROCEDURE	11
8.1 DESCRIPTION	11
8.2 INSTRUCTIONS FOR USE AND ADMINISTRATION	11
8.3 CONTRAINdications	13
8.4 RISKS	13
9. STUDY PROCEDURES	13
9.1 OVERVIEW	13
9.2 RECRUITMENT	14
9.3 SCREENING /VISIT 1 (-30 TO -1 DAYS)	14
9.4 RANDOMIZATION.....	15
9.5 IOVERA° TREATMENT/VISIT 2 (5 DAYS +- 2 DAYS PRIOR TO TKA)	15
9.6 VISIT 3 / TOTAL KNEE ARTHROPLASTY (DAY 0)	16
9.7 STUDY FOLLOW UP	17
9.8 PHOTOGRAPHS.....	20
9.9 STUDY EXIT	20
9.10 SUBJECT DISCONTINUATION	20
9.11 STUDY TERMINATION.....	20
9.12 STUDY-RELATED ASSESSMENTS.....	21
9.12.1 Knee Injury and Osteoarthritis Outcomes Score (KOOS)	21
9.12.2 Numeric Rating Scale for Pain (NRS for Pain)	21
9.12.3 Subject Satisfaction Questions	21
[REDACTED]	[REDACTED]
10. STATISTICAL METHODOLOGY AND ANALYSES.....	22
10.1 INTRODUCTION	22
10.2 STUDY ENDPOINTS.....	23
10.2.1 Primary Effectiveness Endpoint	23
10.2.2 Secondary Effectiveness Endpoints	Error! Bookmark not defined.
10.2.3 Safety	25
10.3 ANALYSIS COHORTS.....	ERROR! BOOKMARK NOT DEFINED.
10.3.1 Screening Cohort	Error! Bookmark not defined.
10.3.2 Safety/ITT (Intent to Treat) Cohort	Error! Bookmark not defined.

1. BACKGROUND

Total Knee Arthroplasty (TKA) is a highly effective procedure to relieve symptoms in patients with severe arthritis. Improvements in pain, physical function, and enhanced quality of life in patients who have undergone TKA are well established in the literature^{1,2}. However, post-operative pain associated with TKA is severe. Effective pain control following TKA allows for earlier ambulation and initiation of physical therapy, which speeds recovery, reduces hospital length of stay, and decreases the risk of postoperative complications³. The VHA/DoD and the American Society of Anesthesiologists have both issued guidelines suggesting that wherever possible, practitioners should use multimodal pain management⁴. Clinical management of post-op TKA pain should include both pharmacologic and non-pharmacologic modalities and minimize preventable postoperative complications⁵. As demand for primary TKAs is projected to grow to 3.48 million procedures per year by 2030 in the United States alone⁶, the need for effective and economic multimodal pain management has never been greater.

Managing pain via multi-modal strategies, including peripheral nerve blocks, in the inpatient postoperative phase has been shown to decrease opioid consumption⁷, decrease opioid related side effects, decrease hospital stay, and increase time to ambulation^{8,9,10}. Nursing, hospital, and pharmacy utilization in managing PCA, continuous regional nerve blocks, and administration of oral opioid dosing are associated with higher costs of care and introduce sources for staff error^{11,12}. Furthermore, the idea of multi-modal pain management extends beyond the in-patient phase of treatment. Decreasing prescription opioid use during outpatient rehabilitation decreases NSAID and opioid related side effects, especially important among the aging population^{13,14}.

The iovera[°] device introduces a new mode of pain management delivery in TKA. The iovera[°] system uses liquid nitrous oxide contained within the device and closed-end needles to create a precise zone of cold at the target nerve sites. This Focused Cold TherapyTM delivery platform causes a temporary peripheral nerve block based on a process called Wallerian degeneration (2nd degree axonotmesis) without disrupting connective nerve tissue. With nerve conduction blocked, pain is relieved in sensory nerves (nerves that pass impulses from receptors toward or to the central nervous system). Degeneration of the nerve axons is followed by a predictable restoration of nerve function involving axon regeneration from the point of treatment to the distal end of the nerve at a rate of 1.0–1.5 mm a day^{15,16}. Early clinical study results have demonstrated that the duration of effect of iovera[°], when applied to the infrapatellar branch of the saphenous nerve for knee pain, is two to three months; longer than that of other clinically adopted modalities (PCA opioids, single shot regional nerve blocks, continuous regional nerve blocks, extended-release peri-operative local opioids, oral and IV NSAIDs, acetaminophen, and oral opioids). Early clinical data further suggests that iovera[°], when applied to the infrapatellar branch of the saphenous nerve (ISN) and anterior femoral cutaneous nerve (AFCN) prior to TKA, reduces the amount of opioids requested by subjects to maintain similar levels of pain relief¹⁷.

This study is designed to investigate whether iovera[°] treatment prior to TKA decreases cumulative patient opioid use over the course of 6 weeks following TKA while maintaining similar levels of pain relief. The study will also investigate whether there is a relationship between patients treated with iovera[°] and patient reported pain and function as measured by KOOS JR., NRS for Pain, [REDACTED]

2. REGULATORY STATUS

The iovera[°] device is 510(k)-cleared (K133453 and K161835) and is used to destroy tissue during surgical procedures by applying freezing cold. It can also be used to produce lesions in peripheral nervous tissue by the application of cold to the selected site for the blocking of pain. It is also indicated for the relief of pain and symptoms associated with osteoarthritis of the knee for up to 90 days. The iovera[°] system is not indicated for treatment of central nervous system tissue

Additionally, Myoscience and an independent review board have determined that the iovera[°] device is a non-significant risk device under 21 CFR §812.2(b) as described for use within this protocol. Therefore, an approved Investigational Device Exemption (IDE) from FDA is not required to legally perform the study described herein in the US.

3. STUDY OBJECTIVE

To evaluate the outcomes of patients undergoing iovera[°] treatment of the ISN and AFCN prior to total knee arthroplasty to provide temporary postoperative pain relief.

4. STUDY DESIGN

This is a single-site, prospective, randomized trial.

5. DURATION

Each Subject participates for up to 16 weeks. Enrollment is expected to take up to 5 months. Total study duration is expected to be up to 8 months.

6. INVESTIGATOR QUALIFICATIONS

To participate in this study, an Investigator must have an active medical license and board certification in Orthopedic Surgery, Anesthesia, Pain Management, or Physical Medicine and Rehabilitation. The Investigator or designee must undergo training conducted by Myoscience, Inc., on the study device prior to enrolling Subjects in the study.

7. STUDY POPULATION

7.1 Target Patient Population

The target patient population is adult men and women ages 22 to 79 in the United States scheduled to undergo primary unilateral TKA under spinal anesthesia for primary diagnosis of osteoarthritis.

7.2 Subject Eligibility

To be included in the study, Subjects must meet all of the inclusion criteria and none of the exclusion criteria list in **Table 1**.

Table 1. Study Eligibility Criteria.

Inclusion Criteria
1. 22 to 79 years of age
2. Scheduled to undergo primary unilateral TKA under spinal anesthesia for primary diagnosis of osteoarthritis
3. Subject is a class I-III on the American Society of Anesthesiology (ASA) Physical Classification System
4. Anticipation of discharge to home after inpatient acute post-op phase based on age, comorbidities, home environment, and social support are in favor of discharge to home in the opinion of the Investigator.
5. Subject is willing and able to give written informed consent.
6. Subject is fluent in verbal and written English.
7. Subject is willing and able to comply with study instructions and commit to all follow-up visits for the duration of the study.
8. Subject is in good general health and free of any systemic disease state or physical condition that might impair evaluation or which in the Investigator's opinion, exposes the Subject to an unacceptable risk by study participation.
Exclusion Criteria
1. Chronic opioid use (defined as daily or almost daily use of opioids for >3 months).
2. Concurrent painful physical condition, surgery, or musculoskeletal disease that requires analgesic treatment during study follow-up that is not strictly related to the target knee being treated with iovera°, which have the potential to confound the postoperative assessments (e.g., significant pain from other joints, chronic neuropathic pain, concurrent or planned contralateral TKA, concurrent foot, neck, spine, hip, or other musculoskeletal disease, arthritis, or planned surgery, etc.).
3. Greater than 15° malalignment (varus or valgus) on pre-operative radiograph.
4. Previous Myoscience treatment.
5. Previous Partial or Total Knee Arthroplasty. Partial or Total Knee Arthroplasty of the contralateral knee is permitted if surgery was completed at least nine (9) months prior to Screening.
6. Body Mass Index ≥ 40
7. Prior surgery in the treatment areas that may alter the anatomy of the infrapatellar branch of the saphenous nerve (ISN) or the anterior femoral cutaneous nerve (AFCN) or result in scar tissue in the treatment area.
8. Any clotting disorder and/or use of an anticoagulant (e.g. warfarin, clopidogrel, etc.) within seven (7) days prior to administration of the device. Low dose aspirin (81mg or less daily) for cardiac prophylaxis allowed.
9. Any local skin condition at the treatment sites that in the Investigator's opinion would adversely affect treatment or outcomes.
10. Open and/or infected wound in the treatment areas.
11. Allergy to lidocaine.
12. History of cryoglobulinemia
13. History of paroxysmal cold hemoglobinuria.
14. History of cold urticaria.
15. History of Raynaud's disease.
16. History of opioid or alcohol abuse.
17. Subject is pregnant or planning to become pregnant while enrolled in the study.

- 18. Current enrollment in any investigational drug or device study or participation within 30 days prior to screening.
- 19. Currently being treated for related knee injury under worker's compensation claim or equivalent (i.e. legal case).
- 20. Any chronic medical condition that in the Investigator's opinion would prevent adequate participation.
- 21. Any chronic medication use (prescription, over-the-counter, etc.) that in the Investigator's opinion would affect study participation or Subject safety.
- 22. For any reason, in the opinion of the Investigator, the Subject may not be a suitable candidate for study participation (i.e., history of noncompliance, drug dependency, etc.).

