9.3 Screening /Visit 1 (-30 to -1 days)

A patient who signs the informed consent document will be considered a study Subject. A Subject who withdraws from the study prior to randomization will not count toward the study's sample size. Potential participants will be screened for eligibility against **Table 1**.

Once the informed consent form is signed, the Subject is assigned a study number. The Subject number is comprised of the 2-digit site number followed by a consecutively assigned 3-digit Subject number that starts with 001. For example, the first screened Subject for site 01 will be assigned study number 01-001. The Subject number is the identification number used on CRFs and other study documents throughout the study. In the event a Subject withdraws from the study, their Subject number cannot be reassigned to any other Subject.

The Investigator, or designee, will document the Subject's medical history, demographic information, obtain vital signs and complete an assessment of the intended treatment areas and concomitant medications/concurrent procedures. Subjects will be asked to bring all prescription opioid bottles to all study follow-up visits. A pill count will be completed by the study coordinator, or designee.

Once a Subject has been determined to meet all inclusion and none of the exclusion criteria, the Subject will complete the following:

Assessments:

- NRS for Pain when standing from a seated position in target knee
- KOOS JR. (English version 1.0)

|

[REDACTED]

Physical Performance Measures in the following order:

- Timed Get Up and Go Test

Subjects may be complete Screening / Visit 1 and iovera[°] Treatment / Visit 2 on the same day.

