9.4 Randomization

After meeting all of the inclusion and none of the exclusion criteria and prior to study treatment, Subjects will be randomized in a 1:1 manner to either:

- **iovera[°] Treatment:** Subject undergoes treatment with the study device using study supplied Smart Tip.
- **Standard of Care Treatment:** Subject does not undergo iovera[°] Treatment

The Investigator or designee will record the randomization assignment in the source documentation and CRF. Any Investigator who is discovered to tamper with randomization will be immediately terminated from the study.

9.5 iovera[°] Treatment/Visit 2 (5 Days +- 2 days prior to TKA)

Medical history will be reviewed as well as concomitant medications and procedures. Blood pressure and heart rate will be assessed. The Investigator, or designee, will reconfirm all eligibility criteria are met.

The iovera[°] device will be prepared by the trained Investigator (or Sponsor designee) according to the **User Guide**. If at any time the device does not perform as expected the Investigator (or designee) will follow procedures as outlined in the **User Guide**.

Prior to the initiation of the iovera[°] treatment, the Investigator, or designee, will mark the treatment lines on the knee to be treated as shown in Figure 2 located in section 8.2.

Then the skin along the treatment lines will be cleansed with alcohol. Lidocaine, no epinephrine, will be injected along the treatment lines superficially in order to achieve cutaneous anesthesia and to the bottom of the subcutaneous layer, atop the fascia, to temporarily block conduction of the infrapatellar branch of the saphenous nerve and the anterior femoral cutaneous nerve.

Once localized anesthesia of the treatment lines and the nerves is achieved, the Investigator, or designee, will complete the iovera[°] treatment along the treatment lines. Regardless of the length of treatment lines (width of patella or from lower pole of the patella down to tibial tubercle), adjacent insertions are placed along the treatment lines until the entire line has been treated so all Subjects receive the same treatment. Treatment is not to be modified or influenced by any Subject response to changes in knee pain. Representatives of Myoscience, Inc. may be present during the treatment. Photos of the treatment area may be taken.

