10.4 Study Endpoints

10.4.1 Primary Effectiveness Endpoint

The primary effectiveness endpoint is the cumulative consumption of opioids from the time of hospital discharge to 6 weeks post-TKA Surgery. Opioid consumption will be converted to morphine equivalents, and subject consumption will be verified by pill count at follow-up visits. The cumulative morphine equivalent will be divided by the number of days to provide the Total Daily Morphine Equivalent (TME) for the subject.

The difference in the mean TME between the two treatment groups will be calculated as Standard of Care TME mean – Active TME mean, such that a positive difference indicates that the Standard of Care Treatment group had a larger mean TME than the Active Treatment group, while a negative difference indicates the opposite. A positive difference between the two treatment groups reflects a positive outcome for the study.

Let $\mu_{1,Active}$ and $\mu_{1,SOC}$ denote the true mean TMEs for the active and standard of care treatments, respectively. Then the null and alternative hypotheses for the primary effectiveness endpoint are as follows:

$$H_0: \mu_{1,Active} \geq \mu_{1,SOC}$$

$$H_1: \mu_{1,Active} < \mu_{1,SOC}$$

A one-sided, two-independent sample, Satterthwaite t-test will be used to test the null hypothesis. The Primary Effectiveness Study Objective will be met if this t-test is statistically significant using a one-sided $\alpha = 0.025$ level of statistical significance.

This endpoint will be summarized by treatment group using descriptive statistics. The difference in mean TMEs between the two treatment groups and a 95% confidence interval based on the t-distribution for the true difference in the mean TMEs between the two treatments will also be provided.

The database will be “soft-locked” after all 6 week data has been collected (all data monitored with the exception of data points collected beyond 6 weeks). An interim analysis of the primary endpoints will be performed on the soft-locked data for internal Myoscience purposes. The full dataset will be locked upon completion of all visit and adverse event follow-ups and this data will be reported in the clinical study report.

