### **5.2 Adjustments for Covariates**

No adjustments for covariates will be made.

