## **5.7 Examination of Subgroups**

No subgroup analyses are planned.

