## 8.0 EFFECTIVENESS ANALYSES

### 8.1 Primary Effectiveness Endpoint

The primary effectiveness endpoint is the cumulative consumption of opioids from the time of hospital discharge to 6 weeks post-TKA Surgery. Opioid consumption will be converted to morphine equivalents (see Appendix 2 for conversion factors), and subject consumption will be verified by pill count at follow-up visits. The cumulative morphine equivalent will be divided by the number of days to provide the Total Daily Morphine Equivalent (TME) for the subject.

The difference in the mean TMEs between the two treatment groups will be calculated as Standard of Care TME mean – Active TME mean, such that a positive difference indicates that the Standard of Care Treatment group had a larger mean TME than the Active Treatment group, while a negative difference indicates the opposite. A positive difference between the two treatment groups reflects a positive outcome for the study.

Let  $\mu_{1,Active}$  and  $\mu_{1,SOC}$  denote the true mean TMEs for the active and standard of care treatments, respectively. Then the null and alternative hypotheses for the primary effectiveness endpoint are as follows:

$$H_0: \mu_{1,Active} \geq \mu_{1,SOC}$$

$$H_1: \mu_{1,Active} < \mu_{1,SOC}$$

Missing data for this endpoint will be imputed using multiple imputation methods. First, the relatively uncommon, non-monotone missing data will be imputed using the MCMC option of SAS® PROC MI. For this endpoint, the imputation model will include a term for treatment and the pill counts at visits 4, 5, and 6. Second, the monotone missing values will be imputed using the chained equation method by SAS® PROC MI option MONOTONE REG. For each subject within each imputed dataset, the value of the endpoint will then be determined. The imputed data sets will each be analyzed to obtain the difference in means between treatments and the corresponding standard error, and the results will be summarized using PROC MIANALYSE. A one-sided t-test will be used to test the null hypothesis. The Primary Effectiveness Study Objective will be met if this t-test is statistically significant using a  $\alpha = 0.025$  level of statistical significance.

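### The primary opioid comparison and its imputation use no baseline variable, although recent opioid users are eligible and medication history is recorded at Screening: precision is forgone and chance imbalance goes uncorrected, but the test is valid

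*Protocol*

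**What the plan says.** **Who can enter.** Exclusion 1 in Protocol 7.2 (Table 1) is "Chronic opioid use (defined as daily or almost daily use of opioids for >3 months". Daily use of 3 months or less passes it, as does intermittent use of any length. Other criteria narrow the population without setting an opioid dose or duration. Exclusion 2 covers other painful conditions that need analgesics, and exclusion 16 covers a history of opioid or alcohol abuse. Exclusion 21 is "Any chronic medication use (prescription, over-the-counter, etc.) that in the Investigator's opinion would affect study participation or Subject safety", and exclusion 22 leaves general suitability to the investigator, with drug dependency as an example.

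**What is recorded before treatment.** At Screening (Protocol 9.3) staff document medical history and "complete an assessment of the intended treatment areas and concomitant medications/concurrent procedures". NRS pain is also taken at Screening.

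**Allocation.** Protocol 9.4 says "Subjects will be randomized in a 1:1 manner to either" of the two arms. Neither it nor SAP 3.2 names a stratification factor.

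**Primary analysis.** Protocol 10.4.1: "A one-sided, two-independent sample, Satterthwaite t-test will be used to test the null hypothesis". SAP 8.1 pools a difference in means and its standard error over imputed datasets. SAP 5.2 states "No adjustments for covariates will be made", and SAP 5.7 states "No subgroup analyses are planned".

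**Imputation.** For TME, SAP 8.1 says "the imputation model will include a term for treatment and the pill counts at visits 4, 5, and 6". No baseline variable is named.

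**Baseline table.** SAP 7.0 and Table 1.1 summarise age, gender, ethnicity and race. The public text shows no tabulation of pre-operative opioid use by arm.

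**The concern.** The primary endpoint is opioid consumption after discharge, which has no Screening value of its own. Opioid use before surgery is the nearest baseline measure, and exclusions 1 and 16 show that the sponsor considers opioid history relevant. Because the criteria admit non-users and recent users together, some of the TME variance is likely to come from that history.

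The plan ignores it in three places. The treatment difference is not adjusted for it. A subject with no post-operative counts is imputed from treatment arm alone, even if known to be a recent user. The baseline tables shown would not reveal an imbalance. The stake is the precision of the primary estimate, and how far a reader can trust it if one arm of about 60 happens to contain more recent users.

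**Working it through.** **Inputs from the documents.** SAP 3.4: difference 12.0 mg/day, SDs 18.2 (iovera) and 26.0 (standard of care), one-sided 0.025, 57 evaluable per arm, about 60 randomised per arm. Protocol 10.8 gives an iovera SD of 16.9 with the same 57. The SAP values are used here because they come closer to 57.

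**1. The plan's own figure.** Satterthwaite t-test, noncentral t:
- SAP SDs: 56 per arm needed for 80%; power at 57 is 80.7%.
- Protocol SDs: 54 per arm needed; power at 57 is 82.4%.
- SE at 57 per arm = sqrt((18.2² + 26.0²)/57) = sqrt(1007.24/57) = 4.20 mg/day. At 60 per arm it is 4.10.

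These SDs are total SDs, so any variation due to prior use is already inside them.

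**2. Assumed inputs.** The documents give neither the share of users p nor the user-minus-non-user gap D. The main range is p = 10-40% and D = 10 mg/day, the same in both arms.

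**3. Formulas.**
- Mean variance = (331.24 + 676)/2 = 503.62.
- R² = p(1-p)D²/503.62.
- Adjusted power: both SDs multiplied by sqrt(1-R²), 57 per arm.
- SD of the between-arm difference in user share, 60 per arm = sqrt(2p(1-p)/60).
- Shift in the TME difference at a 1.96-SD imbalance = 1.96 × that SD × D.

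**4. Results for D = 10 mg/day.**

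| p | R² | Adjusted power | SD of imbalance | Shift (mg/day) |
|---|---|---|---|---|
| 0.10 | 0.018 | 81.4% | 0.055 | 1.1 |
| 0.20 | 0.032 | 81.9% | 0.073 | 1.4 |
| 0.30 | 0.042 | 82.3% | 0.084 | 1.6 |
| 0.40 | 0.048 | 82.6% | 0.089 | 1.8 |

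A shift of 1.1-1.8 mg/day is about 0.26-0.43 of the SE at 60 per arm (1.07/4.10 and 1.75/4.10).

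**5. Larger gaps, 20-40% users.** D = 15 with p = 0.2 gives R² 0.071 and power 83.5%. D = 20 with p = 0.3 gives 0.167 and 87.2%. D = 25 with p = 0.4 gives 0.298 and 92.1%. The 1.96-SD shifts are 2.2, 3.3 and 4.4 mg/day.

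**6. Are larger gaps plausible?** Reading N=40 in Protocol 9.6 as 40 tablets and using SAP Appendix 2: oxycodone 40 × 5 × 1.5 = 300, tramadol 40 × 50 × 0.1 = 200, total 500 morphine mg. Over 42 days that is 500/42 = 11.9 mg/day. Gaps of 15 and 25 mg/day equal 630 and 1050 mg over 42 days, more than the whole listed supply. This is not a hard ceiling. SAP Listing 4 has a column for refills, and the planned difference of 12.0 mg/day is itself just above 11.9.

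**7. Validity.** Simulation with 30% users, D = 12, 60 per arm, SAP SDs, 60,000 runs:
- Over all randomisations: type I error 0.025, power 82.5%.
- Given 10 points more users in standard of care: 0.044 and 91%.
- Given 10 points more users in iovera: 0.010 and 74%.

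The overall error rate is held. The conditional figures show what adjustment would remove.

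**The case against.** The strongest reply is that an unadjusted, prespecified comparison is a legitimate choice. Randomisation makes it valid, its sample size was computed for that test, and the planned 95% interval already covers chance imbalance. All of that stands, and it rules out two stronger readings that a reader might draw:

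- *That the primary estimate is biased or its error rate inflated.* Overall type I error is 0.025. A 1.96-SD imbalance is by definition a 5% event counting both directions, and its effect is part of an SE of about 4.2 mg/day.
- *That the trial is underpowered.* Power at 57 per arm is 80.7% without adjustment. The gain is on top of that.

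A third reading, that imbalance could move the result by about a third of the planned effect (4.4/12.0 = 37%), needs 40% users together with a 25 mg/day gap. The documents support neither figure, and that gap would require refills well beyond the listed supply.

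The imputation point is also modest. The plan allows for few missing primary values (120 randomised against 114 required), and multiple imputation draws around the arm's distribution and does not assign a single average.

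Two practical objections also stand. No look-back window or field for opioid dose or duration before surgery is described, so a yes/no item must be defined from the medication record. And SAP 8.2 already reports many missing responses on one KOOS JR. item, so some data had been seen when it was written; replacing the primary model of an unblinded trial late would cost credibility.

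None of this explains why baseline information on the endpoint, already collected, is left out of the estimate, the imputation and the baseline table.

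**Conclusion.** The point holds as a matter of efficiency and robustness. Recent opioid users are eligible, their history is recorded, and the primary TME analysis does not use it. The planned test is valid and reaches about 80% power, so the loss is precision forgone and an imbalance that would be neither corrected nor, in the tables shown, displayed.

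With 10-40% users and a 10 mg/day gap, the gain is about 1 to 2 points of power (80.7% to 81.4-82.6%), and a 1.96-SD imbalance moves the difference by 1.1-1.8 mg/day, or 9-15% of the planned 12.0. With 20-40% users and gaps of 15-25 mg/day, power would be 83.5-92.1%; refills make such gaps possible, but nothing in the documents shows them. Both p and D are assumptions. No gain is claimed for Screening NRS pain, because the documents give no correlation with TME.

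**What to change.** 1. **SAP 5.2 and 8.1.** In each imputed dataset, estimate the treatment difference from a linear model of TME on treatment, pre-operative opioid use (yes/no, derived from the Screening concomitant-medication record) and Screening NRS pain, with a heteroscedasticity-consistent SE. Name which of the two NRS questions in Protocol 9.12.2 is used. Pool the estimate and SE in PROC MIANALYZE, as SAP 3.5 already does, and report the unadjusted difference as supportive.
2. **SAP 5.3 and 8.1.** Add the same two variables to the primary imputation model.
3. **SAP 7.0 and Table 1.1.** Tabulate pre-operative opioid use by arm.
4. **Timing.** If outcome data by arm have already been seen, including through the internal 6-week analysis in Protocol 10.4.1, keep the unadjusted analysis as primary and label the adjusted one a sensitivity analysis.
5. **Protocol 9.4 and SAP 3.2.** Stratify the randomisation on this yes/no factor only if enrolment has not begun.

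The cost is one defined yes/no item with its derivation rule, a slightly longer model specification and two degrees of freedom. No extra visits or subjects are needed. A yes/no factor treats occasional and daily use alike, so it will recover only part of the information.
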